Improvement of Patient Satisfaction and Overall Outcomes Using HealthLoop

NCT03481595

07/30/2019

Introduction and Background:

The Problem

• Health systems invest significant resources in their efforts to improve quality and reduce costs. The patient is often left out of this equation.

• Studies have shown that when patients are engaged, they take increased responsibility for their own health, and play more active roles in prevention.

• Because physicians have strong relationships with their patients, they are in the best position to encourage patient engagement. However, physicians need frictionless tools with minimal implementation barriers in order to facilitate this relationship during follow-up.

Patient engagement has been referred to as the next blockbuster drug, and increasing evidence demonstrates that highly engaged patients experience improved outcomes as well as reductions in complications, readmissions, and total costs of care than patients who are not actively involved in his/her care. While these engagement-related outcomes have been shown in primary care, preventive care, and mental health specialties, relatively little has been done to explore this relationship in orthopedics. An estimated \$1.5 billion is spent annually in the US on readmissions following orthopaedic procedures, highlighting the opportunity to impact and improve orthopaedic outcomes. While some readmissions are planned and/or unavoidable, many can be attributed to patient health status, poor discharge planning, and non-optimized care coordination.

GetWell Loop is a SaaS platform that allows physicians to monitor signs and symptoms, and communicate with patients during the postoperative recovery process. The platform enables doctors to identify patients at risk of decline in the follow up period. Patients are engaged through mobile and web-based surveys, reminders, and information personalized to the patient's specific condition or treatment plan. The company's platform also collects patients' feedbacks and monitors status against expected progress. Alerts are sent to physicians or providers about patients who are at risk of treatment failures, complications, or hospital readmissions. Physicians are informed if patients are trending toward an adverse outcome based on the patient's responses. Along with helping to prevent readmissions, GetWell Loop can also help institutions collect patient-reported outcomes (PROs) data, which can be used to evaluate and improve quality measures.

GetWell Loop and the Cleveland Clinic are interested in collaborating on a clinical pilot study to demonstrate that high patient engagement leads to enhanced pre-operative preparation potentially reducing length of stay (LOS), readmissions / reoperations, discharge disposition to home rather than another facility, reduced need for in-person follow up, increased patient (and provider) satisfaction, and increased satisfaction survey completion rates after elective primary hip and knee arthroplasty (THA and TKA). These improvements can translate on higher financial savings through the episode especially in light of the alternative payment models.

Specific Aims: GetWell Loop is currently used by orthopedic groups around the country, and is believed to improve peri-operative outcomes after THA and TKA and mitigate risk by: 1. Enhancing patient engagement with providers, 2. Allowing patients to play an integral role in patient-reported outcomes, 3. Generating and relaying actionable pre- and post-operative reporting directly to the clinical team, and 4.

Detecting impending post-operative complications early, enabling timely intervention and preventing avoidable complications and readmissions.

The specific aims of this proposal are to:

- 1. Measure the impact of using GetWell Loop on patient (and provider) satisfaction
- 2. Understand the degree to which high post-operative engagement reduces the need for in-person or telephone follow up appointment time
 - a. Does the use of GetWell Loop lead to fewer potentially avoidable healthcare utilization encounters such as Emergency Department and hospital visits (including readmissions and reoperations)?
 - b. Does utilizing GetWell Loop improve clinical workflow by minimizing telephone calls and thereby offloading support staff, allowing them to be more efficient?
 - c. Does utilizing GetWell Loop reduce the volume of on call pages by addressing patient questions up front, alleviating concerns, and providing them with the information they need when they need it?
 - d. Does utilizing GetWell Loop allow the practice to identify patients whose inperson follow up needs are minimal, thereby freeing new referrals slots and enhancing same-day access?
 - e. Does GetWell Loop improve the throughput of patients by eliminating unnecessary follow-up appointments?
- 3. Measure length of stay, discharge disposition (home versus extended care facility) and 90 days readmission and reoperation rates
 - a. Does the early detection of adverse signs/symptoms that develop between clinical encounters result in earlier intervention that thereby reduces readmission and reoperations?
 - b. Do Patient Reported Outcomes (PROs), collected at intervals between clinical encounters, provide useful information which facilitates the detections of post-acute complications prior to the next clinical encounter?
 - c. Does patient adherence to instructions as well as recommended activity levels, captured through continuous activity monitoring such as the Jawbone Up Band (a wristband capable of measuring activity), predict time to recovery, functional outcomes, and potential failure rates? (optional)
- 4. Evaluate the financial impact of GetWell Loop in the episode of care

Methods: The study design is a prospective randomized trial in which patients undergoing selected hip and knee orthopedic procedures will be offered peri-operative use of GetWell Loop vs standard care. Approximately 300 patients will be enrolled (150 in each group).

Phase 1: 6 month run-in with 9 month follow (total of 12 month long study). Will collect the following outcome measures:

- Demographics (Age, gender, BMI)
- Comorbidities
- Surgery details (Length of surgery, laterality, surgeon)
- LOS and discharge disposition
- Number/length of follow up visits within 90 days (in person and telephone)
- 90 days readmission and reoperations
- Patient and provider satisfaction survey completion rates
- Patient satisfaction (VAS scale and PPE-15)

Phase 2: 3 months for statistical analysis and writing manuscript.

Study Participants

- A. Patients Total Hip and Total Knee Arthroplasty patients treated at Avon Hospital
 - a. Inclusion criteria
 - i. Primary THA or TKA patient
 - ii. Personal consent to participate
 - iii. Have internet access or mobile access with a valid email address at the time of enrollment
 - iv. Above the age of 18 and are capable of consent
 - v. English speaking patient
 - b. Exclusion criteria
 - i. Staged arthroplasty procedure within 6 months of the index procedure
 - ii. Abandoned email address of record (e.g. bounce of email from clinic). If so, then data may be censored in the pilot analysis
 - iii. Less than 14 days until scheduled surgery

iv. Outpatient surgery

Data Analysis Plan

The difference in percent of respondents indicating a problem on the PPE-15 between treatment and control groups will be calculated as [percent of standard of care respondents reporting a problem, averaged across all PPE-15 domains] – [percent of GetWell Loop respondents reporting a problem, averaged across all PPE-15 domains], such that a positive difference indicates that the GetWell Loop group was more satisfied than the standard of care group, while a negative value indicates the opposite. A superiority hypothesis test using the two-independent sample t-test will be used to statistically evaluate the difference in the average satisfaction between groups. All other outcomes will be analyzed using chi-square tests for categorical variables and t-tests for continuous variables. Regression analysis will be conducted for multivariate analysis.

Schedule of Events

Evaluation	History	IntraOp	90 days postop	90 days	1 year
	/ PreOp		(Chart Review)	postop	(study completion)
				(survey)	
Demonstration	V				
Demographics	Λ				
Medical	X				
History/Comorbidities					
		V			
Surgical Details		X			
Discharge (LOS, disposition)			Х		
Track				Х	
Readmission/Reoperation					
Track ED visits, office visits				Х	
Track calls and on-call pages				Х	
Adverse Events			Х	Х	
Patient Satisfaction				Х	
VAS and PPF-15					
Provider Satisfaction Survey					Х

Study Metrics

Metric	Justification
Patient satisfaction VAS and PPE-15 (attached)	-Substantial opportunity for the Cleveland Clinic to differentiate itself among health systems and enhance revenue associated with patient satisfaction measures
Physician and staff satisfaction	- Opportunity to demonstrate clinical adoption rates and low barriers to implementation.
Total 90 day post-operative cost from index date+1 (same day) or from index date + LOS (inpatient)*	GetWell Loop templates should be able to either prevent the complication, or through early detection at the clinic level, reduce expense through minimized emergency room visits and readmissions.
*Claims submitted within 90 days must be limited to ICD-10s listed below (or to hospitalization due to ICD-10s below) in order to exclude unrelated claims.	
90 day post-op hospitalization rate (this is a readmission if initially an inpatient procedure, or an admission if initially an outpatient procedure)*	
*Must be associated with ICD-10s listed below in order to exclude unrelated readmissions.	
90-day ED Visit Rate* *Must be associated with ICD-10s listed below in order to exclude unrelated ED visits.	
Number of follow up visits within 90 days	Demonstration to physicians and practices the potential to improve throughput and workflow efficiency by minimizing the number of follow up visits required.
Potentially preventable readmissions	Potentially preventable admissions, events, ED visits. Using an approach similar to 3M's

Potentially Preventable Events grouping software, we will examine all events (ED visits, admissions, complications) for relation to index event, and compare this rate to prior year. Data may be
supplemented by Physician survey.
http://solutions.3m.com/wps/portal/3M/en_US/H ealth-Information-Systems/HIS/Products-and- Services/Products-List-A-Z/PPR-and-PPC-Grouping- Software/

ICD-10 codes for relevant metrics

Description		ICD-10
1.	Must be in 1 st or 2 nd diagnosis and must not be chronic, or	
2.	If patient is admitted, must be in 1 st or 2 nd diagnosis on hospital discharge.	
Infection and inflammatory reaction due to internal prosthetic device, implant, and graft		
•	Due to unspecified implant, device, and graft	T8579XA
•	Due to internal joint prosthesis	T8450XA
•	Due to other internal orthopedic device, implant and graft	T8460XA
Other	complications of internal prosthetic device, implant, and graft	
•	Due to unspecified implant, device, and graft	T859XXA
•	Due to internal joint prosthesis	T8481XA-
•	Due to other internal orthopedic device, implant, and graft	T8486XA; T8489XA; T849XXA
Postoperative infection		K6811
•	Other post-operative infection (abscess, septicemia)	T814XXA
Disrup	tion of wound	

Dehiscence of operation wound	T8130XA-
	T8132XA
Infections of Skin and Subcutaneous Tissue	
Upper arm and forearm	
Leg except foot	
Abscess NOS, Cellulitis NOS	
	10391
Gastrointestinal hemorrhage	
Hematemesis	К920
Melena	K921
Hemorrhage of gastrointestinal tract, unspecified	K922
Hemorrhage NOS	R58
Venous embolism and thrombosis of deep vessels of lower extremity	182409
Of unspecified site	18291
Pulmonary embolism and infarction	12690
	12692
	12699
	18281/A,
Since FD coding is often not as precise as the above, we will likely need to also	102010A
have these below	
Fever unspecified	R502
	R509
	R5081-
	R5094
Sustamia inflammatary recogness sundrome due to infectious process without	R6883
systemic inflammatory response syndrome due to infectious process without	A419
acute organ dysrunction	
Severe sepsis	R6520
Joint Replacement DRGs	461-462,
	469-470
Hip and Knee specific DRGs	466-468,
	488-489

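### Aim 1 promises an impact on provider satisfaction, but the plan describes one end-of-study provider survey and nothing to compare it with

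*Combined protocol and SAP*

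**What the plan says.** Aim 1, under Specific Aims, is to "Measure the impact of using GetWell Loop on patient (and provider) satisfaction". Introduction and Background lists, among the results the pilot is meant to demonstrate, "increased patient (and provider) satisfaction, and increased satisfaction survey completion rates".

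The rest of the plan bears on providers as follows.

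- **Methods.** The design is a prospective randomised trial in which "patients undergoing selected hip and knee orthopedic procedures will be offered peri-operative use of GetWell Loop vs standard care". About 300 patients are to be enrolled, 150 per group. No allocation or grouping of providers is described.
- **Methods, Phase 1 outcome list.** The only provider entry is "Patient and provider satisfaction survey completion rates". Satisfaction itself is listed for patients (VAS and PPE-15).
- **Study Participants.** Patients are the only category defined.
- **Schedule of Events.** The row "Provider Satisfaction Survey" carries one mark, in the column for 1 year (study completion).
- **Data Analysis Plan.** The PPE-15 contrast between patient groups is spelled out. Then: "All other outcomes will be analyzed using chi-square tests for categorical variables and t-tests for continuous variables".
- **Study Metrics.** Physician and staff satisfaction is justified as "Opportunity to demonstrate clinical adoption rates and low barriers to implementation". A historical comparison appears only in the row on potentially preventable readmissions, where events are to be examined "for relation to index event, and compare this rate to prior year".

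**The concern.** An impact, or an increase, is a difference between two quantities: satisfaction with the platform and satisfaction without it. For patients the randomised arms supply both. For providers the plan describes one measurement at the end of the study and no second quantity.

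A favourable score at 1 year, reported under Aim 1, would invite the reading that the platform raised provider satisfaction. The described data could not separate that from satisfaction that was already high before the study began. The same survey serves the adoption purpose given in Study Metrics perfectly well. The mismatch is between the wording of the aim and the data to be collected, and it should be settled before results are reported.

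**Working it through.** The main check is textual: look for each kind of comparator that could turn a provider score into an effect.

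| Possible comparator | Where it would appear | What is there |
|---|---|---|
| Baseline survey of the same providers | Schedule of Events | No mark before the 1-year column |
| Concurrent provider group without the platform | Methods; Study Participants | Only patients are allocated, and only patients are defined as participants |
| Separate ratings by each provider for the two patient arms | Phase 1 outcome list; Data Analysis Plan | Not described |
| Earlier-period provider scores | Study Metrics | Prior-year comparison is for preventable events only |
| A provider contrast in the analysis | Data Analysis Plan | General sentence on chi-square and t-tests; no provider groups named |

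Result: 1 scheduled provider survey, 0 described comparators.

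The general analysis sentence nominally covers provider satisfaction as one of the other outcomes. A chi-square test or t-test between groups needs two groups, and the only groups the plan defines are the patient arms. Nothing says that providers divide along those arms, so the sentence does not identify what provider scores would be compared with.

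The plan gives no provider-level figure to reproduce. Its 300 patients have no bearing here, because providers are a different unit and their number is not stated. The calculations below therefore use assumed counts of 10, 15 and 20 and serve only as context.

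**Precision of the single survey as planned.** The 95% confidence half-width for the mean, in SD units, is t(0.975, n−1)/√n.

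- n = 10: 2.262/3.162 = 0.72
- n = 15: 2.145/3.873 = 0.55
- n = 20: 2.093/4.472 = 0.47

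This is precision for a level. No number of respondents turns it into precision for a change.

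**Detectable change if a baseline survey were added.** This describes an optional redesign, not the flaw. For a paired t-test at two-sided 0.05, the detectable mean change d, in SDs of the change, is the value at which a noncentral t with n−1 degrees of freedom and noncentrality d√n gives 80% power.

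- n = 10: d = 1.00
- n = 15: d = 0.78
- n = 20: d = 0.66

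**The case against.** The strongest reply is that the provider questionnaire is not in the text available. One end-of-study survey can contain comparative items, for instance asking a provider to rate work with GetWell Loop patients against work with standard-care patients. With patients randomised and one hospital named, the same providers may well have treated both arms, although the document does not say so. This part stands: comparative items cannot be ruled out. It limits the claim to what the plan describes, and the plan describes no such contrast and no analysis of one. If the items exist, the plan should name them and say how they will be analysed.

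A second reply is that the Schedule of Events follows a patient's course from the pre-operative visit onward, so a provider baseline has no natural column. That weakens the inference from a blank cell. But the 1-year provider mark was fitted into the same table, and no other section mentions a provider baseline.

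Third, the statement about increased satisfaction is background to a pilot and reads as a hypothesis, and provider satisfaction is in parentheses even in Aim 1. This is fair as to weight. It is still in the first numbered aim, and describing provider satisfaction is just what a pilot can do, which is the rewording proposed.

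Fourth, the assumed respondent counts have no basis in the document, and if every provider at the site answers, a sampling interval means little. Both points are accepted; the conclusion does not rest on those figures. It is also true that the general analysis sentence is thin for most outcomes, but the others can at least be compared between patient arms.

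**Conclusion.** The concern holds. Followed exactly, the plan yields a level of provider satisfaction at study end and no described contrast: one survey, no comparator. That fits the adoption purpose in Study Metrics. It does not support the language of impact in Aim 1 or of an increase in Introduction and Background.

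The conclusion rests on the text alone and on no numerical assumption. Its one limit is the unseen questionnaire. Confidence is high that no provider comparison is described. The consequence is contained: the randomised comparison, the patient part of Aim 1 and the sample size are untouched. It should be corrected because an aim that its own data cannot answer is likely to be over-read when reported.

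**What to change.** **Preferred.** Restate Aim 1 as the impact on patient satisfaction. Report provider satisfaction, provider survey completion and adoption descriptively, with confidence intervals and the number of providers approached and responding. Remove increased provider satisfaction from the results to be demonstrated. This needs no new data; it gives up a provider-effect claim that the described plan cannot support.

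**Only if the sponsor wants to keep a provider effect.** Give the same short survey to the same providers before the first patient is enrolled and again at study completion. Analyse the paired change, and report it as a non-randomised before-after result. The cost is one extra short questionnaire. The result stays open to time trends, and precision is low with few providers: at an assumed 10, 15 or 20, only changes of about 1.00, 0.78 or 0.66 SD of change would be detectable with 80% power. If enrolment has already begun, a true baseline is no longer available and the descriptive wording is the one to use.

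### Aim 2a asks one pooled question about avoidable acute encounters, but the plan names no comparison of that quantity between the randomised arms, and its only pooled rate is set against the prior year

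*Combined protocol and SAP*

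**What the plan says.** Aim 2a (Specific Aims) asks whether use of the platform leads to "fewer potentially avoidable healthcare utilization encounters such as Emergency Department and hospital visits (including readmissions and reoperations". Aim 3 separately calls for 90-day readmission and reoperation rates.

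Methods sets the size: "Approximately 300 patients will be enrolled (150 in each group". The Phase 1 outcome list has "90 days readmission and reoperations" as one item and does not list ED visits. The Schedule of Events does include ED visits, on a different row from readmission and reoperation.

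The Study Metrics table has a "90-day ED Visit Rate" and, as its own row, a "90 day post-op hospitalization rate (this is a readmission if initially an inpatient procedure, or an admission if initially an outpatient procedure". Both are limited to a code list; for ED visits the note reads "Must be associated with ICD-10s listed below in order to exclude unrelated ED visits". Reoperation has no row there. The Potentially preventable readmissions row holds the only pooled rate: "we will examine all events (ED visits, admissions, complications) for relation to index event, and compare this rate to prior year".

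The Data Analysis Plan details the PPE-15 comparison and covers the rest with one rule: "All other outcomes will be analyzed using chi-square tests for categorical variables and t-tests for continuous variables". It names no composite, total encounter count or lead utilisation outcome.

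**The concern.** The trial randomises patients so that differences in outcome can be attributed to the platform. For Aim 2a, the one pooled rate the plan describes gives that up. A prior-year comparison mixes any platform effect with whatever else changed between the years, such as discharge practice, case mix, coding or staffing.

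It also compares unlike patients. Trial participants must consent, speak English and have internet or mobile access with a valid email address. They must be at least 14 days from surgery, have no staged procedure within 6 months and not be outpatient cases. Nothing says the prior-year group would be restricted in the same way. The row does not say either whether the trial side is the GetWell Loop arm or both arms together.

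At stake is the answer to a stated aim. The team could report a fall against last year as a platform effect while the concurrent controls fell just as much. Without a pre-specified pooled outcome, it could also choose after the fact which utilisation result stands for Aim 2a.

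**Working it through.** **1. Is there a randomised comparison of the pooled quantity?**

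| Place | Content | Pooled? | Comparator named |
|---|---|---|---|
| Specific Aims, 2a | ED and hospital encounters, with readmissions and reoperations | Yes | None |
| Specific Aims, 3 | Readmission and reoperation rates | No | None |
| Methods, Phase 1 list | Readmission and reoperations, one line | ED visits absent | None |
| Study Metrics, hospitalisation and ED rows | Two rates, each limited by ICD-10 code | No | None |
| Study Metrics, Potentially preventable readmissions | ED visits, admissions, complications | Yes | Prior year |
| Data Analysis Plan | Generic tests for all other outcomes | No outcome named | Groups, by implication |

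The only row that is both pooled and has a named comparator uses the prior year. No row pairs the pooled quantity with the standard-care arm.

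**2. What would a randomised composite give at this size?**

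The plan has no figure to reproduce: it states no event rate, effect size, alpha or power. From the documents: n = 150 per arm. Assumed: two-sided 5% test; control rates of 10% (ED visit), 4% (readmission) and 2% (reoperation); risk halved.

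The composite control rate depends on overlap:
- fully nested: the largest component, 10%
- independent: 1 − 0.90 × 0.96 × 0.98 = 15.3%, taken as 15%
- disjoint: 10 + 4 + 2 = 16%, an upper bound

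Exact power sums Bin(x; 150, p_C) × Bin(y; 150, p_T) over all pairs with z² > 3.841. Here z = [(x − y)/150] / √[2p̄(1 − p̄)/150] and p̄ = (x + y)/300.

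| Outcome | Control v treated | Power |
|---|---|---|
| Reoperation | 2% v 1% | 9% |
| Readmission | 4% v 2% | 16% |
| ED visit, or fully nested composite | 10% v 5% | 37% |
| Composite, partial overlap | 13% v 6.5% | 48% |
| Composite, near independent | 15% v 7.5% | 55% |

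Normal-approximation check, with power = Φ{[d − 1.96√(2p̄q̄/n)] / √(p_Cq_C/n + p_Tq_T/n)}:
- 10% v 5%: (0.0500 − 0.0596)/0.0303 = −0.317, giving 0.375
- 15% v 7.5%: (0.0750 − 0.0715)/0.0362 = 0.096, giving 0.538

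For a 30% reduction, power is 15% from a 10% base, 19% from 13% and 21% from 15%. Power of 80% for a halving needs a control rate of about 25%, where 152 per arm are required.

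**3. Precision of the risk difference**

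The 95% half-width is 1.96√(p_Cq_C/150 + p_Tq_T/150):
- 10% v 5%: 5.0 ± 5.9 percentage points
- 15% v 7.5%: 7.5 ± 7.1 points
- 15% v 10.5%: 4.5 ± 7.5 points

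The code restriction removes events, so if these assumed rates are all-cause, the restricted outcome would have lower rates and less power.

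**The case against.** **The generic rule already covers it.** One could argue that the chi-square rule for all other outcomes supplies the between-arm comparison. It does for outcomes defined between arms. The pooled rate has its own stated comparator, the prior year, and nothing tells the analyst to set that aside.

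**Separate outcomes serve Aim 3.** This stands. Readmission and reoperation rates are a stated aim, so a composite should not replace them or become the only permitted utilisation test.

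**An any-event composite is not what Aim 2a asks.** This stands in part. The aim concerns potentially avoidable encounters, so an all-cause outcome would drop the plan's relatedness restriction and could dilute an effect. A yes/no outcome per patient also simplifies a question about numbers of encounters. Applying the ICD-10 rule, with all-cause as a sensitivity analysis, meets the first objection; the second is an accepted simplification.

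**It is a pilot, and satisfaction has the only detailed analysis.** This limits the weight of the point. But the introduction says the study is meant to demonstrate effects that include readmissions and reoperations, and the comparator problem does not depend on sample size.

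**A stronger reading.** A reader might infer that the plan runs three separate chi-square tests, each on an event too rare to be informative, and that pooling would repair this. The documents do not support that. Three tests are only an inference from a generic rule, and readmission and reoperation share one line. No event rates are given, so rarity is an assumption. Pooling adds no power if events are fully nested, and about 19% to 21% power for a 30% reduction is still low.

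**Conclusion.** The point holds as a gap in definition and comparator. Aim 2a poses a pooled question, no randomised comparison of the pooled quantity is named, and the one pooled rate is written against a historical year. That conclusion rests on the text alone.

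The size of the resulting bias cannot be worked out, because the documents give neither prior-year data nor expected rates. The gain in power from a composite over ED visits alone runs from nothing (37% v 37%) to about 18 percentage points (37% v 55%). This assumes component rates of 10%, 4% and 2%, a halving of risk and a two-sided 5% test. The case for the change is therefore a valid comparator and one pre-specified estimate, not adequate power: 150 per arm remains too few for moderate effects at these rates.

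**What to change.** In the Data Analysis Plan and the Potentially preventable readmissions row of Study Metrics:

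- Define one patient-level outcome for Aim 2a: at least one ED visit, readmission or reoperation within 90 days that meets the plan's ICD-10 relatedness rule. State how the rule applies to reoperation, which has no row of its own. Add the all-cause version as a sensitivity analysis.
- Compare it between the GetWell Loop and standard-care arms as randomised, with a risk difference and 95% CI.
- Keep any prior-year comparison as descriptive only, and say which trial patients it uses.
- Keep the separate readmission and reoperation rates for Aim 3, reported with CIs so that a non-significant result is not read as no effect.
- Show the components beneath the composite, and add ED visits to the Phase 1 outcome list.

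The cost is a few lines of text, with no added patients; ED visits, readmissions and reoperations are already to be tracked to 90 days. The downside is that ED visits will probably dominate the composite, and its gain over ED visits alone depends on overlap and event rates not yet known.

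### Aim 4 asks for the platform's financial impact, but the only cost metric is complication-related 90-day claims, which would not capture the platform's own cost

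*Combined protocol and SAP*

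**What the plan says.** Aim 4, the last of the Specific Aims, is a single line: "Evaluate the financial impact of GetWell Loop in the episode of care". It names no method, cost components or perspective (payer, hospital or practice).

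The Study Metrics table holds the only cost measure: "Total 90 day post-operative cost from index date+1 (same day) or from index date + LOS (inpatient", with the closing bracket and an asterisk following. The note to the asterisk says: "Claims submitted within 90 days must be limited to ICD-10s listed below (or to hospitalization due to ICD-10s below". The codes, listed at the end of the document, cover infection, wound disruption, bleeding, thromboembolism, fever, sepsis and similar events. The justification given is that the templates will prevent complications or, by early detection, "reduce expense through minimized emergency room visits and readmissions".

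The Introduction and Background describes the intervention: "GetWell Loop is a SaaS platform that allows physicians to monitor signs and symptoms". It also anticipates the direction of the result: "These improvements can translate on higher financial savings through the episode".

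Workload is recorded in the Phase 1 outcome list as "Number/length of follow up visits within 90 days (in person and telephone" (closing bracket omitted), and calls and pages appear in the Schedule of Events. No unit cost is attached to any of these. Cost itself is in neither the Phase 1 list nor the Schedule of Events. In the Data Analysis Plan it falls under the general sentence that assigns t-tests to continuous outcomes.

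**The concern.** The randomised comparison is the platform against standard care, so any cost of providing the platform falls on one arm. A licence fee, set-up cost or staff time spent on alerts is not a claim with a complication diagnosis. The metric therefore records what the platform may save downstream but not what it costs to provide.

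A t-test on this metric asks whether mean claims cost differs from zero between arms. A reader of Aim 4 is likely to want to know whether any reduction exceeds the cost of obtaining it. The planned analysis cannot separate those two cases, and the omission can only favour the platform. The satisfaction comparison is not affected.

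**Working it through.** The plan states no figure for platform cost, expected saving or cost variability, so there is none to reproduce. The check is a search of the text for cost components, an identity, and an illustration on assumed inputs.

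**1. What enters the cost comparison**

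| Component | In the plan's cost metric? |
|---|---|
| Claims under listed ICD-10 codes, or hospitalisation due to them, within 90 days | Yes |
| Platform fee and set-up | No; not mentioned anywhere |
| Staff time handling alerts | No; not mentioned as a cost |
| Calls, pages, follow-up visits | Recorded or tracked, with no unit cost |
| Index stay (LOS) | No; for inpatients the window opens after it |
| Discharge disposition | Recorded, with no costing step |

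The metric omits the platform's cost. It also omits several benefits that the plan hopes for.

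**2. Identity**

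Let S be mean claims cost under standard care minus mean claims cost under GetWell Loop, and c a constant platform cost per patient randomised to GetWell Loop.

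- Net difference = S − c.
- Break-even is at c = S.
- Adding a constant to every patient in one arm leaves the variance unchanged, so SE(S − c) = SE(S).

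**3. Illustration (all dollar inputs assumed)**

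Take 5–10% of standard-care patients with a qualifying event, $10,000–$20,000 per event, and a 20–30% relative reduction.

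- Lowest S: 0.05 × 10,000 × 0.20 = $100.
- Highest S: 0.10 × 20,000 × 0.30 = $600.
- c = $100 takes 100/600 = 17% to 100/100 = 100% of S.
- c = $200 takes 200/600 = 33% to 200/100 = 200% of S.

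With S = $100, net is +$50 at c = $50, $0 at c = $100 and −$100 at c = $200.

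**4. Precision on the same assumptions**

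The plan says "Approximately 300 patients will be enrolled (150 in each group" (closing bracket omitted), so n = 150 per arm. With a fixed cost k per event and at most one event per patient, the 95% half-width is 1.96 × k × √{[p₁(1 − p₁) + p₂(1 − p₂)]/150}.

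- p₁ = 0.05, p₂ = 0.035 (30% reduction), k = $10,000: 1.96 × 10,000 × √[(0.0475 + 0.033775)/150] ≈ $456. Here S = 0.015 × 10,000 = $150, so the break-even fee is $150, with limits 150 ± 456, or −$306 to $606.
- p₁ = 0.10, p₂ = 0.08 (20% reduction), k = $20,000: 1.96 × 20,000 × √[(0.09 + 0.0736)/150] ≈ $1,295. Here S = 0.02 × 20,000 = $400, with limits 400 ± 1,295, or −$895 to $1,695.

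Variation in cost per event would widen both intervals.

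**The case against.** The strongest reply is that Aim 4 is limited to the episode of care, and the background mentions alternative payment models. Read as episode spending, a vendor fee may lie outside the question. The documents do not say that the clinic buys the platform, or that any fee is charged in this pilot. Nor do they tie Aim 4 explicitly to the claims metric. All of this stands. It narrows the point to an unstated perspective and an uncosted intervention, but does not remove it. Several of the plan's stated motives are the provider's own (revenue, throughput, offloading staff), and from that viewpoint the platform's cost belongs in the account. If a payer view is meant, the plan needs to say so.

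A second objection is that charging the whole fee and pilot set-up against this metric would be unfair to the platform. The metric starts after the index stay and leaves out LOS, disposition and staff time. It would also set a provider's expense against payers' claims. This stands, and it is why a net figure should not become the sole Aim 4 result.

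Third, the assumed fees are small beside the sampling error. On the assumptions above, a saving whose interval excludes zero needs an estimate above about $456, so a $100–$200 fee would not turn that estimate into a loss. This also stands, and the dollar illustration carries little weight. The fee could still change the inference: an estimate just above $456 has a lower limit just above zero, and a $200 fee moves that limit to about −$200.

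A reader might go further and infer that claims can never contain a platform cost, that any observed difference is a gross saving, or that the plan would report a net loss as a saving. The documents do not support these readings. They show only that this code-restricted metric would not capture the cost. The difference could be nil or an increase, it is not the full gross episode effect, and the plan contains no reporting rule.

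**Conclusion.** The point holds in limited form. The plan's only cost metric is complication-related 90-day claims, and no other part of the document adds the cost of a platform given to one arm. Followed exactly, the plan can estimate a difference in those claims but cannot tell a net saving from a net cost.

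The size is unknown, because neither the claims difference nor the platform cost is given. What is firm is the identity: a platform cost per patient above the claims difference reverses the sign.

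The conclusion rests on two inferences: that the claims metric is the one meant for Aim 4, since no other cost source is named, and that the platform has a cost to someone, even if it is waived here. This is a cheap, worthwhile improvement to one aim, not a threat to the trial's main comparison.

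**What to change.** In Study Metrics and the Data Analysis Plan:

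1. State the perspective for Aim 4 (payer, hospital or practice) and name the cost metric that serves it.
2. Report the between-arm difference in mean claims cost with its confidence interval, labelled as complication-related 90-day claims cost excluding platform cost.
3. Beside it, report the break-even platform cost per patient, which is that difference with its interval limits. This works even if the fee is confidential or waived. Where a fee is available, a net difference can be given instead, assigning a constant per-patient platform cost to everyone randomised to GetWell Loop.
4. State that the net figure is not the institution's full profit or loss, because index-stay LOS, discharge disposition and staff time are outside the metric.

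The cost is a few sentences and, for the net version only, one cost figure. No extra patients are needed on this account, because a constant fee shifts the estimate without changing its standard error. The downside is a less favourable headline saving.
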